- a. Fasting lab results at enrollment are needed to determine baseline values. Participants that were referred to a weight management clinic at any of the participating sites may have had these labs drawn as part of their routine care. These results will be abstracted from the medical record if they are within 8 weeks of consent date. However, a research blood draw will be done at enrollment if these labs were not done as part of the participant's routine care. If the consent visit takes place virtually/by mail, the participant will be expected to travel to CHLA for a baseline research blood draw.
- b. All arms will have a follow up research blood draw at months 6 and 18.
- c. Each research blood draw will collect approximately 5 mL (1 teaspoon) of blood via venipuncture that will be used for the following testing: HbA1c, Total Chol, LDL, HDL, TG, AST/ALT, Glucose and insulin.

6. All participants

*Visit 1: if consenting via mail, these procedures will be completed at the 2nd session as visit 1 will be split in 2

** Each participant will have the opportunity to earn up to \$200 in gift cards for participation in this study: up to \$50 for participation in the intervention at 3 and 6 months and \$50 for going to the last 2 study visits (at 12 and 18 months). The amount of payment will be based upon how much of the intervention the participant completes.

***Visit 2 and 3 must occur within a 4-week period (+/- 2 weeks from the 3- or 6-month date) and Visits 4 and 5 must occur within an 8-week period (+/- 4 weeks from the 12- or 18-month date).

Study Visit Schedule for Group 3 (In-Clinic) (total visits = 9)

*Visit 1: if consenting via mail, these procedures will be completed at the 2nd session as visit 1 will be split in 2

The youth participants in this group will also earn up to \$50 at 3 months (visits 4) and 6 months (visit 7) for participation in the 6-month intervention and \$50 for completion of study visits 8 and 9.

The table below depicts the assessment time points and key measures.

Month	0	3	6	12	18
Covariates					
Co-Morbidities, race/ethnicity, household composition, socioeconomic status, and previous weight loss programs completed	x				
Primary Outcomes (Aim 1)					
Height, Weight, zBMI, %BMIp95	x	x	x	x	x
Secondary Outcomes / Mediators (Aims 2, 3)					
Youth Surveyed: Yale Food Addiction Scale-Children	x	x	x	x	x
CES-D	x	x	x	x	x
Perceived Stress Score	x	x	x	x	x
BRIEF 2	x				
ASRI	x	x	x	x	x
Food Craving Questionnaire	x	x	x	x	x

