Binge-Eating Disorder Screener	x		x	x	x
Satisfactory Survey			x		x
Physical Activity Questionnaire	x	x	x	x	x
SF-12	x	x	x	x	x
EQ5D	x	x	x	x	x
S-Weight	x		x		
Parent Surveyed:					
Demographic (Including Fast Food Consumption)	x				x
Height, Weight BMI	x	x	x	x	x
Health Encounters	x	x	x	x	x
Satisfactory Survey			x		x
Fasting Lab Tests: HbA1c, Total Chol, LDL, HDL, TG, AST/ALT, Glucose, Insulin	x		x		x

Post Study Follow-up Options:

1. After completion of the 6-month interventions participants will be offered the following choices for continued care:
 - a. Participants in groups 1 and 2 will have access to use the mobile app without coaching upon completion of the 6-month intervention. However, a participant owned iPhone is required in order to use the mobile app. Group 3 will have access to use the mobile app without coaching upon

completion of the study (post 18 month). Participants will have to own an iPhone in order to use the mobile app as it is an IOS App only.

2. All participants will receive a call from a study team member monthly for the 18-month study period.
 - a. They will discuss weight trends since the intervention completion and any interim health encounters (ED visits, hospitalizations, PMD visits, changes to medical history).
 - b. They will also discuss if any interim weight management strategies have been utilized or started.
3. All Participants will have an in person/virtual follow up 12 months and 18 months post consent (baseline) where a repeat weigh in and survey completion will occur. All participants will also have a fasting research blood draw at 6 and 18 months.

Enrollment and Retention:

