To evaluate the effect of the intervention arms on amount of physical activity performed by the youth, each youth will complete the physical activity questionnaire and recall their activity level over the last 7 days at each study visit.

Measurements (~ 1.5 hour to complete)

1. **Yale Food Addiction Scale (YFAS-c, 25 questions, ~7 minutes):** The YFAS-c is a validated measure of addictive-like eating behavior based on the Diagnostic and Statistical Manual of Mental Disorder V diagnostic criteria for substance dependence^{19, 25, 26}. Intervention participants will complete the YFAS-c at consent and at 3, 6, 12 and 18 months.

2. **The Center for Epidemiologic Studies Depression scale (10 questions, ~5 minutes):** The CES-D is a short self-report measure used to measure depressive symptoms in the general population²⁰. The scale demonstrates strong internal consistency (Cronbach's $\alpha > 0.85$), moderate test-retest reliability (>0.50), and moderate validity ($r > 0.50$)²⁰. This will be completed at all in person / WebEx study visits 0,3,6,12, and 18.

3. **The Perceived Stress Scale (14 questions, 10 minutes):** The PSS measures subjective perceptions of distress in one's own life situations. Based on Lazarus' transactional model of stress and coping, the PSS assesses how well a person feels they can cope with stressors, rather than measuring the nature of the stressors themselves. The measure has demonstrated strong reliability ($r > 0.80$) and validity in social and health science studies²¹. This will be completed at all in person/ WebEx study visits 0,3,6,12, and 18.

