8. Behavior Rating Inventory of Executive function 2 (55 questions, 15 minutes)²²: The Behavior Rating Inventory of Executive Function (BRIEF2) provides theoretically and empirically derived clinical scales that measure aspects of executive function. The clinical scales form broad indices of behavior and cognition and an overall score, the global executive composite (GEC)²². This will be completed at baseline only.

9. Food Cravings Questionnaire (FCQ, 15 questions, ~5 minutes)²⁴: Scores on the FCQ-T have been found to be positively associated with eating pathology, body mass index (BMI), low dieting success and increases in state food craving during cognitive tasks involving appealing food stimuli. This will be completed at all in person/ WebEx study visits 0,3,6,12, and 18.

10. Binge Eating Disorder Screener (BEDS-7, 7 questions, 4 minutes): This questionnaire is utilized to screen for binge eating disorders. This will be completed at in person/ WebEx study visits 0,6,12, and 18.

11. Physical Activity Score (PAQ, 12 questions, 4 minutes): This instrument was developed to assess general levels of physical activity for adolescents 14-19 years of age.²⁷ This will be completed at all in person/ WebEx study visits 0,3,6,12, and 18.

12. SF-12 Health Survey (12 questions, 3 minutes): The SF-12 is a practical, reliable and valid measure of physical and mental health. It is particularly useful in large population health surveys or for applications that combine a generic and disease-specific health survey. This will be completed at all in person/ WebEx study visits 0,3,6,12, and 18.

13. EQ5D (15 questions, 4 minutes): EQ-5D is a standardized instrument for measuring generic health status. It has been widely used in population health surveys, clinical studies, and economic evaluation and in routine outcome measurement in the delivery of operational healthcare. This will be completed at all in person/WebEx study visits 0,3,6,12, and 18.

14. S-Weight (5 item questionnaire, 3 minutes): S-Weight is a tool used to determine the individual's stage of change. This allows the research team to assess and monitor motivation and readiness for change to determine if baseline levels promote success in the intervention.

Adherence and Retention

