The Clinic Intervention will utilize the Kids N Fitness Curriculum and will address the following topics over the 6-month intervention:

Session 1: Nutrition and Food Groups

Session 2: Portion Power

Session 3: Real Foods, Fat and Fiber

Session 4: Sugar Savvy

Sessions 5: Healthy Shopping, Healthy Eating

Sessions 6: Special Occasions and Moving Forward

Those youth randomized to the in-clinic control arm will complete the intervention at CHLA or virtually via WebEx. The participant and their parent/guardian will meet with each team member for 20-30 minutes to discuss the topic of the session. The youth will participate in some mild physical activity exercises, such as stretching. Treatment fidelity strategies will be utilized for all three intervention arms to ensure the accurate and precise delivery of each arm as intended. (See Treatment Fidelity Below).

Example Follow up Phone Calls Curriculum Outline (AppCoach):

Call	
1	Introduction: --Coach introduction --Curriculum introduction --Problem Food Identification --Goal setting
2	Personal Motivation: Identify personal motivation and goals of each participant. Have participant identify in and out of home barriers to weight management success. Problem Food Withdrawal Instruct to complete personal story
3	Problem Food Withdrawal -Assess barriers to compliance

4	Problem Food Withdrawal Progress
5	Introduce Snacking Elimination. Identify period of time to start withdrawal Problem Food and Snacking Withdrawal
6	Problem Food and Snacking Withdrawal
7	Problem Food and Snacking Withdrawal
8	Problem Food and Snacking Withdrawal
9	Continue PF and Snacking Withdrawal start food amount reduction Evaluate current barriers to weight management success. Have participant identify one goal to achieve over the next 4 weeks
	Introduce food weigh AppCoach and App: Distribute App setup instructional video
10	Progress report on above. Review frequency of eating out. Review missed weighed meals
11	Review progress, compensation and points earned. Identify successes and barriers. Make goals for second half of intervention
12	Review Face to Face / WebEx Visit 2 Goal of withdrawing from all 10 PF by week 12
13	Review maintenance PF avoidance. Encourage to consider assigning additional PF as tolerated
14	Goal of eliminating snacking by week 14
15	Review maintenance of PF and snacking avoidance

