The primary outcome will be change in zBMI and excess BMI percent over the 95th percentile (%BMI_{p95}) compared to baseline, assessed at 3, 6, 12 and 18 months, both within the groups and compared between groups and in clinic group. For analysis over time, the Δ%BMI_{p95} (BMI percentile – 95th percentile), which is the distance (in kg/m²) from the 95th percentile, will be utilized³¹.

Secondary outcomes will include: compliance with App intervention, retention rates with scheduled phone calls and clinic visits, ASRI, BRIEF, Satisfaction survey, YFAS-c, fasting lab testing compared pre and post intervention. Collected lab studies will include: HbA1c, Lipid Panel, AST/ALT. Each of these lab tests are currently recommended for routine clinical care screening every 6-12 months in obese adolescents³.

An estimated cost analysis will be completed to determine the cost per patient to implement the 6 month AppCoach intervention, App alone intervention and multi-disciplinary in-clinic intervention (Clinic)³². Cost Analysis to include: time or expenses saved compared to in-clinic (travel, missed work or school); efficiency of clinic and staffing needs, including appointment duration and physical space requirements, and health care utilization rates and costs of care^{33, 34}.

Analytic Plan:

Power and Sample Size Estimates:

The power analysis is prepared for comparing (1) the difference in the mean change of zBMI and %BMIp95 between baseline, 6 months, and 18 months across App+Coach, App, and Clinic, (2) the difference in zBMI and %BMIp95 mean change between App+Coach and Clinic, and (3) the difference in zBMI and %BMIp95 mean change between App+Coach and App. Review of the literature revealed that the majority of studies utilize the change in zBMI to evaluate the effectiveness of weight management interventions in adolescents. However, Freedman et al. and the CDC have proposed utilizing alternative metrics for weight change such as %BMIp95 which may be more strongly associated with change in body size in adolescents. Therefore, both metrics were considered in the power calculation to further explore their use as outcome measures in youth with obesity and severe obesity.

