Statistical analysis: All statistical analyses were conducted in accordance with the planned study protocol.¹⁹ We estimated that 180 participants (60 in each group) would provide 89% power ($\alpha = 0.05$, 2 sided), to detect an effect size of 0.29 which corresponds to a difference of 4.0% %BMIp95 between the three groups. Analyses followed principles of intention-to-treat (ITT) and were performed in nQuery + nTerim 4.0 and Stata/SE 17 (StataCorp, College Station, TX). A two-sided significance level of 0.05 was utilized throughout the analyses. Our analysis approach is based under the assumption that data are missing at random, therefore, imputation using last observation was carried forward, and multiple imputation based on logistic regression model (for BEDS-7 scores only) were utilized to account for missing data. Results from the ITT analysis using imputation were compared as per protocol analysis with completed data. For all outcomes a per-protocol analysis was conducted for: full-program (completed full 24-week intervention period), pre-COVID (completed 24-week intervention prior to 3/15/2020), and during COVID (completed 24-week intervention after 3/16/2020). In addition, to account for impacts of the intervention dosage received on each primary outcome measure we conducted an analysis of participants who were adherent to at least 80% of the prescribed intervention modalities versus those who were nonadherence. Participants' demographic characteristics and baseline anthropometric measurements were reported as appropriately, mean and standard deviation or median and interquartile range for continuous variables, and frequency and percentages for categorical variables. The change in %BMIp95 between week 24 and baseline was assessed using analysis of variance (ANOVA) for all participants via ITT, per-protocol, PreCOVID and during COVID. First, the %BMIp95 was analysed in log scale mixed-effects linear regression model to assess the association between change in %BMIp95 and demographic characteristics (sex, ethnicity,

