obesity related co-morbidities), CED-SC, PSS, BRIEF-2, YFAS-c, and BEDS-7 scores univariately and adjusting for recruitment site as a covariate. Then, a multivariable mixedeffects linear regression model was utilized to examine the effect of the possible factors on change in %BMIP95 accounting for recruitment site, demographic and other measured characteristics. The results are expressed in percent change with its associated 95th% confidence interval and p-value.

Data management and quality assurance

Principles underlying our approach to quality control includes: (1) standardization of measurements; (2) use of clear and specific protocols for all study activities including training for data collection and processing; (3) validation and verification of data management procedures by using of software capable of checking for out-of-range values and other sources of outliers; (4) implementation of a data cleaning protocol; and (5) periodic meetings and progress reports to provide specific, well-documented feedback to the investigators concerning potential difficulties as well as sufficient follow-up to ensure that problems are resolved in a timely fashion. Confidentiality will be strictly maintained during all data management. Children's Hospital of Los Angeles Biostatistics Core, Saban Research Institute, will follow aforementioned schemes to collect and manage with maintaining consistent quality and security of the study observations.

Data Collection Management Plan AppCoach:

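### BEDS-7 and CES-D have no stated between-arm comparison, and no BEDS-7 is scheduled between baseline and month 6

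*Combined protocol and SAP*

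**What the plan says.** **Schedule.** On BEDS-7, Measurements item 10 reads: "This will be completed at in person/ WebEx study visits 0,6,12, and 18". The "Binge-Eating Disorder Screener" row of the assessment-time-point table agrees, with month 3 blank. On CES-D, Measurements item 2 reads: "This will be completed at all in person / WebEx study visits 0,3,6,12, and 18".

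**Role.** The assessment-time-point table puts both instruments under the heading that begins "Secondary Outcomes / Mediators (Aims 2, 3". The outcomes table under Initial Visit lists neither. The Outcomes section also lists neither: "Secondary outcomes will include: compliance with App intervention, retention rates with scheduled phone calls and clinic visits, ASRI, BRIEF, Satisfaction survey, YFAS-c", followed by the fasting laboratory tests.

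**Analysis.** The mixed-effects model in Statistical Analysis is fitted "to assess the association between change in %BMIp95 and demographic characteristics". The scores enter it as further explanatory variables, in a list that ends "BRIEF-2, YFAS-c, and BEDS-7 scores univariately". The only other statistical mention of BEDS-7 is that its missing values are multiply imputed.

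**Exposure.** Under App Intervention Groups, both app arms are asked to abstain from self-selected problem foods, to eliminate snacking, to weigh the food served at meals while the app reduces amounts, and to weigh themselves daily. The example AppCoach call outline starts food-amount reduction at call 9, while the other two components continue. At call 12 it sets this target: "Goal of withdrawing from all 10 PF by week 12". The snacking target follows at week 14.

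**The concern.** The app arms are built on food restriction in adolescents. Among the listed measures, BEDS-7 is the only binge-eating screener and CES-D the only depression scale. They are therefore natural places to look for an unwanted effect of the intervention, and the trial already collects them in every arm.

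The stated analysis asks a different question: whether these scores are associated with weight change. It does not ask whether assignment to AppCoach or App changes the scores relative to Clinic. If the plan is followed as written, the main report could describe weight change by arm without saying whether binge-eating or depressive symptoms moved differently by arm.

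For BEDS-7 there is also a gap in the data. Nothing is recorded between baseline and about the end of the intervention, and a participant lost before month 6 has no post-baseline value. The power section assumes 20% dropout but does not say when it occurs.

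**Working it through.** No sample size, power or error rate enters this point. The check sets the sections side by side and works out visit timing.

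**1. Role of each instrument**

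| Place | BEDS-7 | CES-D |
|---|---|---|
| Outcomes table under Initial Visit | absent | absent |
| Assessment-time-point table | secondary outcome / mediator | secondary outcome / mediator |
| Outcomes section | absent | absent |
| Statistical Analysis | explanatory variable for %BMIp95 change; imputation | explanatory variable for %BMIp95 change |
| Adverse-event, suicidality and monitoring sections | not used | not used |

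Statistical Analysis writes CED-SC; I take this to mean CES-D. One place of four treats the scores as possible outcomes, and none attaches a comparison between arms. ANOVA is named only for change in %BMIp95.

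**2. Visits collected.** BEDS-7: months 0, 6, 12 and 18, so 4 of 5. CES-D: 5 of 5. YFAS-c and FCQ are also taken at month 3.

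**3. Timing against the intervention.** Inputs: a 24-week intervention (Statistical Analysis) and visit windows of 2 weeks either side at months 3 and 6 (outcomes table and visit-schedule notes).

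- Calendar months: month 3 = 3 × 52/12 = week 13, window 11 to 15. Month 6 = 6 × 52/12 = week 26, window 24 to 28.
- Four-week months, as the 24-week points tables and call outline imply: month 3 = week 12, window 10 to 14. Month 6 = week 24, window 22 to 26.

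On either count, the first BEDS-7 after baseline falls between weeks 22 and 28, at about the end of the 24 weeks. On either count, the month 3 window includes weeks 12 and 14, the two target dates in the AppCoach outline.

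**4. Safety sections.** Adverse events are evaluated, graded and summarised annually for all participants. The psychological-risk paragraph covers distress from questions or topics. The suicidality procedure starts from suspicion. None refers to a BEDS-7 or CES-D score, and binge eating is not listed as a risk.

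**5. Survey time at month 3.** From the assessment-time-point table and the minutes in Measurements: YFAS-c 7 + CES-D 5 + PSS 10 + ASRI 15 + FCQ 5 + PAQ 4 + SF-12 3 + EQ5D 4 = 53 minutes. Adding BEDS-7 (4 minutes) gives 57, an increase of 4/53 = 7.5%.

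**The case against.** The strongest reply is that harm is watched for in other ways. Adverse-event monitoring covers every participant, and annual reports must compare event rates with pre-study assumptions. Summary results will include adverse events, and suicidality has its own procedure. Monthly calls in all arms ask about barriers and health encounters, and AppCoach adds weekly recorded calls. CES-D, YFAS-c, FCQ, PSS, SF-12 and EQ5D are all taken at month 3. This stands. A reader might infer that the plan could yield no harm signal at all; the documents do not support that. What remains is narrower: none of these routes uses the two scores or compares them by arm.

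A reader might also infer that month 3 is when withdrawal peaks. The documents do not say so. The week 12 and week 14 dates are targets in an example outline for AppCoach only. Food-amount reduction is the third stage, is gradual and continues in later calls, so cumulative restriction could be greatest nearer month 6. Nor can it be said that a transient rise would certainly be missed, because no recall period for BEDS-7 is given.

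On analysis, the assessment-time-point table does call both scores outcomes or mediators. Statistical Analysis promises per-protocol analyses for all outcomes and gives BEDS-7 its own imputation model. An outcome analysis may have been intended, but it is not stated, and an imputation model serves a covariate equally well.

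Finally, Statistical Analysis is in the past tense, with subgroups split at March 2020, so month 3 visits may be over. That limits the schedule change, not the by-arm table.

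**Conclusion.** The point holds as a cheap improvement. The documents disagree on whether BEDS-7 and CES-D are outcomes, state no between-arm comparison of either, and do not connect either to safety monitoring. The month 3 gap concerns BEDS-7 only: no reading is scheduled from baseline until weeks 22 to 28, depending on how months are counted and where the visit falls in its window.

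The conclusion rests on two assumptions: that CED-SC means CES-D, and that Statistical Analysis describes the analyses in full. That these scores are good places to look for harm is a judgement drawn from what the app arms ask of participants, not a statement in the documents. The documents give no expected rate of positive screens, so nothing can be said about what size of difference the trial could detect. The by-arm table would be for estimation, not for a powered test.

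**What to change.** 1. Reconcile the outcomes table under Initial Visit, the assessment-time-point table and the Outcomes section. Name BEDS-7 (screen status, including new positives among baseline negatives) and CES-D as safety outcomes.
2. In Statistical Analysis, add a by-arm report of both at each collected visit: AppCoach against Clinic and App against Clinic, with 95% CIs. Keep the models that use the scores as predictors of %BMIp95 change, labelled exploratory.
3. Add BEDS-7 at month 3 in all arms where those visits are still to come. If they are over, state as a limitation that no BEDS-7 was taken between baseline and month 6.

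Steps 1 and 2 need no new data and cost a few sentences and one table. Step 3 costs about 4 minutes per participant at an existing visit, on a youth battery of about 53 minutes. The downside is that slightly longer survey.

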This study will enroll 292 patients and equally allocate into 3 groups. All these calculations utilize an estimate of standard deviation of change based on the conservation of correlation of 0.5 between pre and post measurements within each group, based on Analysis of Variance (ANOVA) with two-sided Type I error of 5%. For the first study aim, the difference in the mean change of zBMI and %BMIp95 between baseline, 6 months, and 18 months across App+Coach, App, and Clinic, this study has at least 83% power to detect the effect size of 0.244 with the variance of the group means of 0.0003 for the mean change of zBMI and at least 89% power to detect the effect size of 0.263 with the variance of the group means of 2.903 for the mean change of %BMIp95. For the second study aim, the difference in zBMI and %BMIp95 mean change between App+Coach and Clinic, based on two sample t-test with two-sided Type I error of 5%, this study has 88% to detect an effect size of 0.580 corresponds to the mean difference of pre and post change in zBMI at least 0.040 standard deviation between the two groups and a 92% power to detect an effect size of 0.625 corresponds to the mean difference of pre and post change in %BMIp95 at least 4.08 percent between the two groups. For the third study aim, the difference in zBMI and %BMIp95 mean change between App+Coach and App, based on two sample t-test with two-sided Type I error of 5%, this study has 71% power to detect an effect size of 0.464 corresponds to the mean difference of pre and post change in zBMI at least 0.032 standard deviation between the two groups and a 68% power to detect an effect size of 0.452 corresponds to the mean difference of pre and post change in %BMIp95 at least 2.80 percent between the two comparison groups. Assuming 20% dropout rate, this study will achieve the desired study power of 80% for study aim 1 and 2. (nQuery + nTerim 4.0 and Stata/SE 15.1).

Statistical Analysis

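### The plan ranks no primary metric, visit or contrast, and the Statistical Analysis section does not carry forward the AppCoach vs Clinic and AppCoach vs App comparisons that the power section sizes

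*Combined protocol and SAP*

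**What the plan says.** **Outcomes.** Change from baseline in zBMI and in %BMIp95 are both primary, "assessed at 3, 6, 12 and 18 months, both within the groups and compared between groups and in clinic group". Neither metric, no visit and no comparison is put first.

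**Power and Sample Size Estimates.** Three aims are numbered: the three-group comparison over baseline, 6 and 18 months; AppCoach vs Clinic; AppCoach vs App. Each is sized on both metrics. Aims 2 and 3 are each "based on two sample t-test with two-sided Type I error of 5"%. On numbers, "This study will enroll 292 patients and equally allocate into 3 groups", and "Assuming 20% dropout rate, this study will achieve the desired study power of 80% for study aim 1 and 2". Aim 3 is given 71% (zBMI) and 68% (%BMIp95).

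**Statistical Analysis.** The one written test of change that can be read as a comparison of arms is: "The change in %BMIp95 between week 24 and baseline was assessed using analysis of variance (ANOVA"), run in the ITT, per-protocol, pre-COVID and during-COVID sets. The sentence names no factor; that it compares three arms is inferred from the sample-size sentence just before it, which gives 60 per arm. The section also says "A two-sided significance level of 0.05 was utilized throughout the analyses", and it still speaks of an adherence analysis "to account for impacts of the intervention dosage received on each primary outcome measure", so it does not settle on one primary outcome. The mixed models that follow relate %BMIp95 to participant characteristics and questionnaire scores, "accounting for recruitment site, demographic and other measured characteristics"; arm is not among the terms listed.

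**The concern.** The introduction frames the trial as AppCoach against App and against Clinic. A reader of the plan cannot tell which result decides that question, and the two halves of the document lead to different places.

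- **With the power section's t-tests brought in**, several unranked comparisons at 0.05 could each be reported as the primary result, with no control of the overall error.
- **With the Statistical Analysis section taken as it stands**, a single ITT F test on one endpoint holds 5% (with complete data), but it neither tests nor estimates either AppCoach contrast. A significant F says that some arms differ. It does not say that coaching adds anything to the app.

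**Working it through.** **1. The plan's own power figures.** The t-test power uses noncentrality d·√(n/2) on 2n−2 df; the ANOVA power uses λ = N·f² on 2 and N−3 df; two-sided 0.05 throughout.

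| Comparison | Effect size | Stated | 60/arm | 78/arm | 97/arm |
|---|---|---|---|---|---|
| Aim 2, zBMI | d = 0.580 | 88% | 88.3% | 94.9% | 98.0% |
| Aim 2, %BMIp95 | d = 0.625 | 92% | 92.4% | 97.2% | 99.1% |
| Aim 3, zBMI | d = 0.464 | 71% | 71.3% | 82.1% | 89.5% |
| Aim 3, %BMIp95 | d = 0.452 | 68% | 69.0% | 80.1% | 87.9% |

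Aim 1 at N = 180 gives 83.6% (f = 0.244; stated 83%) and 89.0% (f = 0.263; stated 89%). So the stated powers belong to 60 per arm, not to 292/3 = 97 or to 97 less 20% dropout = 78. That mismatch is a separate matter; here all three sizes are carried.

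**2. If the t-tests are imported: error under the null.** Six tests at one visit (one F and two t-tests on each of two metrics), simulated with normal data. The documents give no correlation between the two change scores, so a range is assumed.

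| Assumed correlation | 60/arm | 78/arm | 97/arm |
|---|---|---|---|
| 0.5 | 17.9% | 17.6% | 17.5% |
| 0.8 | 15.0% | 14.9% | 14.9% |
| 0.95 | 12.3% | 12.5% | 12.5% |

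The two AppCoach contrasts on one endpoint share an arm (correlation 0.5) and give about 9%.

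**3. If they are not imported: what F leaves open.** Differences of 4.08 (AppCoach vs Clinic) and 2.80 (AppCoach vs App) imply means of −4.08, −1.28 and 0 relative to Clinic. Their mean is −1.787, and their variance is (2.293² + 0.507² + 1.787²)/3 = 2.903, the plan's own figure. SD = √2.903/0.263 = 6.48. Simulation with 60,000 replicates:

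| | 60/arm | 78/arm | 97/arm |
|---|---|---|---|
| F significant | 88.9% | 95.8% | 98.5% |
| AppCoach vs Clinic significant | 92.8% | 97.6% | 99.2% |
| AppCoach vs App significant | 65.0% | 76.6% | 85.3% |
| F and AppCoach vs App both significant | 63.8% | 76.1% | 85.1% |
| Share of significant F without AppCoach vs App | 28.3% | 20.5% | 13.6% |
| Share of significant F without AppCoach vs Clinic | 1.1% | 0.4% | 0.2% |

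As a share of all trials, a significant F without AppCoach vs App is 88.9 − 63.8 = 25.1%, 95.8 − 76.1 = 19.7% and 98.5 − 85.1 = 13.4% (13.7% in a check with 400,000 replicates), so about 25%, 20% and 14%.

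**4. Sensitivity to the SD.** The plan's %BMIp95 t-test effect sizes imply SDs of 4.08/0.625 = 6.53 and 2.80/0.452 = 6.19. Over that range the shares of significant F tests are 26-29%, 18-21% and 11-14%. The Statistical Analysis section states an effect size of 0.29. With the same means that gives SD = √2.903/0.29 = 5.88, and shares of 23%, 15% and 9%. That section's figures do not fit together (0.29 at N = 180 gives 94.2% power, not 89%), so both versions are shown.

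**The case against.** Five points can be made for the plan, or against pressing the concern further.

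- **The contrasts are in the document.** A reader of the Statistical Analysis section alone might infer that the trial never names a test of AppCoach against Clinic or App. The power section does: they are aims 2 and 3, with a named t-test for each, and the analysis section says it followed the planned protocol. This stands. The fault is that the contrasts are not carried into the analysis text and come without error control.
- **There is an implied order.** The aims are numbered, 80% power is claimed for aims 1 and 2 only, and the second metric is said to be included to explore its use. That suggests priorities but sets no testing rule.
- **The model terms are not a closed list.** The absence of arm from the mixed models is weak evidence, because the wording leaves room for other factors. The point does not rest on it.
- **The unanswered share is mostly power.** The 28%, 20% and 14% largely reflect limited power for AppCoach vs App, which adding the contrast does not raise. This stands.
- **Two larger readings fail.** Counting 2 metrics × 4 visits × 2 contrasts as 16 independent tests gives 1 − 0.95^16 = 56%, but those tests are strongly correlated. And if coaching adds nothing while both app arms are 1.28 better than Clinic, F is significant in 18%, 23% and 27% at 60, 78 and 97 per arm. These are not false positives, because Clinic truly differs.

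**Conclusion.** The concern holds in this form: metric, visit and contrast are unranked, and the Statistical Analysis section omits both AppCoach contrasts, any zBMI test, any between-arm test at 3, 12 or 18 months, and any multiplicity rule.

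The size depends on the reading. With the t-tests imported, there is about a 12-18% chance of at least one p < 0.05 among six comparisons at one visit, under the null and the assumed metric correlations. Without them, the practical gap is the coaching question: about 28%, 20% and 14% of significant F tests at 60, 78 and 97 per arm leave AppCoach vs App unsupported (23%, 15% and 9% at effect size 0.29). For AppCoach vs Clinic the gap is about 1% or less. These figures assume normal data, equal variances, complete follow-up and the plan's own means; the plan's carried-forward values are not modelled.

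A reader might also infer that week-24 %BMIp95 is the only admissible primary endpoint. The documents do not support that. It is what the analysis section sizes and tests, but the Outcomes section equally allows zBMI or 18 months.

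**What to change.** Reconcile the Outcomes, Power and Sample Size Estimates and Statistical Analysis sections.

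1. **State which metric and visit lead.** This is the sponsor's choice. Label the remaining metric, visits and within-group changes as secondary, and the per-protocol and COVID sets as sensitivity analyses.
2. **Add both contrasts** to the ITT week-24 %BMIp95 ANOVA, with estimates and 95% confidence intervals.
3. **Control their error.** One way is the fixed sequence AppCoach vs Clinic, then AppCoach vs App, each at 0.05, which follows the order of aims 2 and 3. Another is to test both only after a significant omnibus F, which is valid for three arms.
4. **Do not take the arm contrasts from the mixed factor models.** They include scores collected after baseline, such as YFAS-c, a listed mediator. BRIEF-2 should be reconciled as well: the outcomes table under Initial Visit has it as a mediator at every visit, while the later assessment table and item 8 of Measurements have it at baseline only.
5. **State when the hierarchy was set.** The Statistical Analysis section is in the past tense. If results were known, label the hierarchy post hoc; rewording cannot restore prespecification.

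No participants are added. With SD 6.48 and two-sample t-tests, power changes as follows.

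| | No gate | Fixed sequence | Omnibus gate |
|---|---|---|---|
| AppCoach vs Clinic, 60/arm | 92.8% | 92.8% | 87.9% |
| AppCoach vs App, 60/arm | 65.0% | 63.1% | 63.8% |
| AppCoach vs Clinic, 97/arm | 99.2% | 99.2% | 98.4% |
| AppCoach vs App, 97/arm | 85.3% | 85.0% | 85.1% |

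The main price is that AppCoach vs App cannot be claimed as confirmatory if the first test fails.
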